**Open-Label Single-Blind and Placebo-Controlled 24 Week Histology Cohorts:**

Includes statins if the following conditions are met:

1. Subject can be defined as statin naïve or experienced at Screening based on the following definitions:
  - a. **Statin-naïve:** no administration of statins within 3 months prior to enrollment.
  - b. **Statin experienced:** administration of  $\leq 50\%$  of the maximal dose of current statin therapy.
2. Requires a stable regimen for at least 3 months prior to Screening through Week 2.

The following are the acceptable daily doses of currently approved statin therapies, including combination preparations of statins and other lipid-lowering agents.

- Atorvastatin:  $\leq 40$  mg/d
- Fluvastatin:  $\leq 40$  mg/d
- Lovastatin:  $\leq 40$  mg/d (immediate release),  $\leq 30$  mg/d (extended release)
- Pitavastatin:  $\leq 2$  mg/d
- Pravastatin:  $\leq 40$  mg/d
- Rosuvastatin:  $< 20$  mg/d (Note: must be  $<$  not  $\leq$  20 mg/d)
- Simvastatin:  $\leq 40$  mg/d

**9.8 Diet and Activity Control**

Subjects should maintain their normal level of physical activity, diet, and lifestyle throughout the entire study (i.e., will not begin a new exercise program or participate in any unusually strenuous physical exertion).

**9.9 Clinical Evaluations****9.9.1 Liver Biopsy**

Subjects who meet the Screening criteria of an available liver biopsy tissue specimen within 6 months of Screening for the double-blind cohort and 12 months for the single-blind open-label cohort will not be required to undergo a liver biopsy. For the dosing Groups 3 or 4 of the open-label single-blind cohort and for the placebo-controlled 24-week histology cohort, the liver biopsy must be performed within 3 months of Screening in order to serve as the Baseline comparison for the additional Week 12 biopsy. All other subjects will be required to undergo a liver biopsy per the study site's local standard-of-care procedure during the Screening period and prior to randomization. Tissue from all subjects will be prepped and read by a qualified pathologist for review for the absence/presence of NASH. Liver biopsies

with histologically confirmed NASH will be further assessed by a qualified pathologist using the NAS and Fibrosis Score established and validated by the NASH Clinical Research Network (see [Appendix A](#)). Liver biopsies will be assessed for degree of steatosis (0–3), lobular inflammation (0–3), hepatocellular ballooning (0–2), and fibrosis (0–4). The first three components will be added together to determine the NAS that ranges from 0 to 8. Liver biopsies with a NAS of <4 will be considered exclusionary. Subjects with liver biopsies with Stage 0 (no fibrosis) or Stage 4 fibrosis (cirrhosis) will be excluded from this study. For the placebo-controlled 24-week histology cohort, only subjects with Stage 2 or Stage 3 fibrosis will be allowed to enroll into the study.

The Screening and EOT biopsies for dosing Groups 3 or 4 of the open-label single-blind cohort and all subjects in the placebo-controlled 24-week histology cohort will be read by a single central pathologist. The biopsies will be read and scored using the same NASH Clinical Research Network (CRN) scores as the inclusion biopsies. These will be read unpaired and blinded to subject and reported separately from the inclusion biopsy.

For the placebo-controlled 24-week histology, only the Week 24 biopsy results will be blinded to the site and subject. Screening biopsy results will not be blinded. The Week 24 biopsy should be obtained before the last dose of NGM282 with a visit window of -7 days and +3 days.

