#### Open-Label Single Blind Cohort:

- a. NAS of at least 4 with 1 point in each component
- b. Histologic evidence of fibrosis without cirrhosis
  - i. Fibrosis stage 1-3
- c. Liver biopsy within 12 months of Screening.
  - i. Dosing Groups 3 or 4 must have a liver biopsy within 3 months of Screening in order to serve as the baseline comparison for the additional EOT biopsy.

Placebo-Controlled 24 Week Histology Cohort:

- a. NAS of at least 4 with 1 point in each component
- b. Histologic evidence of fibrosis without cirrhosis
  - i. Fibrosis stage 2-3
- c. Liver biopsy within 3 months of Screening in order to serve as the baseline comparison for the additional EOT biopsy.

3. Total liver fat content of  $\geq 8\%$  as measured by MRI-PDFF (MRI may be used for up to 8 weeks from the date of the original scan, including use for re-screened subjects)
4. Insulin-resistant or stable T2D

Double-Blind Cohort:

- a. Stable T2D is defined as HbA1c  $\leq 8.5\%$  at Screening.
- b. Diabetes medications: require a stable regimen for at least 3 months prior to Day 1 and throughout the study.
- c. Insulin resistance will be based on fasting insulin level  $\geq 10\text{uIU/mL}$ .

Open-Label Single Blind:

- a. Stable T2D is defined as HbA1c  $\leq 9.5\%$  at Screening.
- b. Diabetes medications (except GLP1 agonists): require a stable regimen for at least 3 months prior to Day 1 and throughout the study.
- c. GLP1 agonists: require a stable regimen for at least 12 months prior to Day 1 and throughout study
- d. Insulin resistance will be based on fasting insulin level  $\geq 10\text{uIU/mL}$ .

Placebo-Controlled 24 Week Histology Cohort:

Patients with T2D or insulin resistance will be allowed to enroll under the following conditions listed below and patients who do not have T2D or insulin resistance can be enrolled as long as all other criteria are met.

- a. HbA1c  $\leq 9.0\%$  at Screening
- b. Patients taking diabetes medications (except GLP1 agonists) require a “stable” regimen for at least 3 months prior to Day 1 and throughout study.
  - i. GLP1 agonists and pioglitazone: require a stable regimen for at least 12 months prior to Day 1 and throughout the study.

- ii. Stable insulin dosing is defined as reasonable dosage adjustments to maintain glucose control.

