## 12.2 Randomization and Enrollment

For the double-blind cohort, at Day 1 all eligible subjects will be randomized via IWRs to one of the three treatment arms (NGM282 3 mg, NGM282 6 mg, or placebo) in a 1:1:1 ratio. The proportion of subjects with diabetes (categorized on a dichotomous scale) will be balanced across the three groups to ensure an even distribution across the three groups.

Diabetes status for balancing (“no diabetes” or “diabetes”), will be based on medical history, Screening labs, current medications, and clinical assessments.

The single-blind cohort is not randomized. Subjects will initially be enrolled sequentially into dosing Group 1 and enrollment will be continuous within and between each dosing groups. Sequencing of the dosing Groups 2 and 3 will be based on PD and safety parameters from dosing Group 1 and may run in parallel to each other. A fourth optional dosing group may be conducted based on the safety/tolerability, imaging data and histology (dosing Group 3 only) data from the prior 3 dosing groups. Dosing Group 4 will be initiated only after all subjects in Cohort 3 have been enrolled and a minimum of 10 subjects have completed 12 weeks of treatment in order to do a preliminary review of key data. Dosing group sequence and individual subject treatment assignment will be blinded only study subjects throughout the study period.

For the placebo-controlled 24-week histology cohort, at Day 1 all eligible subjects will be randomized via IWRS to one of the two treatment arms (NGM282 1 mg or placebo) in a 2:1 ratio. The Sponsor, study sites, and subjects will be blinded to treatment assignment. The randomization schedule will be stratified by subject’s fibrosis stage 2 or 3 based on the screening qualification liver biopsy.

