#### Secondary Objectives:

- Evaluate the percentage change in absolute liver fat content at EOT.
  - In the open-label single-blind cohort, additional evaluations will be performed at Weeks 6 and 18.
  - In the placebo-controlled 24-week histology cohort, additional evaluations will be performed at Weeks 6, 24, and 30.
- Evaluate the percentage of normalization for liver fat content at EOT.
- Evaluate the change in liver fat content response rate as defined by a  $\geq 5\%$  decrease in absolute liver fat content.
- Evaluate the absolute and percentage changes from Baseline to EOT as well as the percentage of normalization of the following parameters: ALT, AST, triglycerides, bilirubin (total and direct), and GGT. Percentage of normalization will also be investigated for a clinically meaningful threshold for triglycerides.
- Evaluate the absolute and percentage changes from Baseline to EOT of the following:
  - Total cholesterol, HDL-C, LDL-C, triglycerides, and lipoprotein particles
  - FFAs
  - Fasting blood glucose, insulin levels, [REDACTED], and HOMA-IR
  - Pro-C3 and ELF scores (Placebo Controlled 24 Week Histology Cohorts)
  - Body weight, BMI, and waist circumference
  - C4 and serum bile acids
  - Bile-mediated absorption as measured by vitamin D, INR, and fecal fat content
- Evaluate the liver histologic response in Placebo Controlled 24 Week Histology Cohorts
  - Improvement in liver fibrosis by  $\geq 1$  stage by NASH Clinical Research Network (CRN) criteria with no worsening of steatohepatitis

- Resolution of NASH (defined as an NAS score of 0 or 1 for inflammation and 0 for ballooning) with no worsening of fibrosis as determined by the NASH CRN criteria.
- Evaluate the exposure of NGM282 in patients with NASH.
  - In the double-blind and placebo-controlled 24-week histology cohorts, NGM282 exposure will be compared to placebo at 2 hours post-dose at Day 1 and EOT and pre-dose at all on-treatment study visits.
  - In the open-label single-blind cohort, NGM282 exposure will be compared across the dosing groups at 2 hours post-dose at Day 1 and Week 12 and pre-dose at all on-treatment study visits. Additional PK samples will be collected at Baseline and 1, 2, 4, 8, and 12 hours post-dose on Day 1 and Week 6 in a subset of subjects in each dosing group.

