8.2.6. The percentage of liver histologic responders

Responders:

- The subjects who have an improvement in liver fibrosis by ≥ 1 stage with no worsening of steatohepatitis (no worsening of lobular inflammation or hepatocyte ballooning or steatosis grade) from baseline to Week 24.
- The subjects who have complete resolution of NASH (defined as an NAS score of 0 or 1 for inflammation and 0 for ballooning) with no worsening of fibrosis (i.e., no progression of NASH CRN fibrosis stage) from baseline to Week 24.

The difference between proportions observed in each treatment group, along with 95% CIs for the difference between proportions, will be presented. The percentage of responders in each treatment group will be compared using a chi-square test. Fisher exact test will be used if 50% of the cells have expected counts less than 5.

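### NASH resolution is scored without requiring NASH on the central baseline read, so a subject who already meets the criterion can count as a responder without changing

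*Protocol*

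**What the plan says.** **Two reads of the Screening biopsy.** Protocol 9.9.1 has tissue from all subjects "read by a qualified pathologist for review for the absence/presence of NASH". For this cohort the Screening and end-of-treatment biopsies "will be read by a single central pathologist", unpaired, blinded to subject and "reported separately from the inclusion biopsy".

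**What the inclusion read controls.** Protocol 8.1.1, criterion 2, requires "NAS of at least 4 with 1 point in each component" and, for this cohort, fibrosis stage 2 or 3. Protocol 12.2 stratifies by fibrosis stage "based on the screening qualification liver biopsy".

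**The responder rule.** SAP 8.2.6 counts as responders "The subjects who have complete resolution of NASH (defined as an NAS score of 0 or 1 for inflammation and 0 for ballooning". The fibrosis condition attached to this is "no progression of NASH CRN fibrosis stage", judged between baseline and Week 24. The protocol's secondary objectives match: "Resolution of NASH (defined as an NAS score of 0 or 1 for inflammation and 0 for ballooning) with no worsening of fibrosis". Fibrosis stage is the only element explicitly compared with baseline.

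**Populations and baseline.** SAP 8.2 makes the Efficacy Population the main one for secondary endpoints, and SAP 5.3 sets no histology condition for it. Protocol 12.4.6 asks only for valid baseline and end-of-treatment biopsies. SAP 6.2.1 defines baseline as the last valid assessment on or before first dose, which does not choose between two reads of the same tissue.

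**The concern.** Eligibility guarantees ballooning of at least 1 on the inclusion read only. A subject can enter with steatosis 2, inflammation 1 and ballooning 1. On the Appendix A scale, one grade of disagreement on ballooning (few ballooned cells versus none) puts that subject inside the resolution criterion on the central Screening read. If the central Week 24 read also meets it and fibrosis stage has not progressed, the rule as written counts a response although nothing changed.

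Such responders arise in both arms regardless of treatment. They raise the placebo rate and shrink the difference. They also make the reported resolution rates poor inputs for planning later trials, which is a stated use of this cohort in Protocol 12.1.

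**Working it through.** **1. The plan's own figure.** Inputs from Protocol 12.1 and SAP 3.5: 50% versus 15%, 80% power, alpha 0.05 (two-sided per SAP 6.1), 2:1 allocation, 15% drop-out.

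Pooled rate = (0.15 + 2 × 0.50)/3 = 0.3833.

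Placebo n = [1.960 × √(1.5 × 0.3833 × 0.6167) + 0.8416 × √(0.15 × 0.85 + 0.50 × 0.50/2)]² / 0.35² = 20.6, rounded up to 21.

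That gives 21 + 42 = 63 completers, and 63/0.85 = 74.1, rounded up to 75 (25 + 50). The stated size reproduces. Power at 42/21 is 80.8% by normal approximation and 82.3% by exact enumeration of the SAP 8.2.6 test (chi-square, or Fisher when at least half the expected counts are below 5). Exact figures are used below.

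**2. Model.** Let f be the share already meeting the criterion on the central Screening read, and r the chance that such a subject is counted as a responder at Week 24, equal in both arms. Then

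response rate in an arm = (1 − f) × p + f × r,

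with p = 0.50 or 0.15. The difference becomes (1 − f) × 35 points whatever r is. At f = 10% and r = 0.7, active = 0.9 × 0.50 + 0.07 = 52.0%, placebo = 0.9 × 0.15 + 0.07 = 20.5%, difference 31.5 points.

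The documents give neither f nor r. The ranges f = 5–20% and r = 0.6–0.8 are assumptions. The planning rates belong to the composite of fibrosis improvement or NASH resolution, because no rate is stated for resolution alone.

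**3. Results.**

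| f | Difference (points) | Power as written, r = 0.6 / 0.8 | Discordant kept as non-responders | Restricted to at-risk (active/placebo) |
|---|---|---|---|---|
| 0% | 35.0 | 82.3% | 82.3% | 82.3% (42/21) |
| 5% | 33.3 | 77.3% / 77.0% | 78.6% | 80.5% (40/20) |
| 10% | 31.5 | 71.9% / 71.4% | 74.6% | 77.4% (38/19) |
| 15% | 29.8 | 66.3% / 65.8% | 70.4% | 74.1% (36/18) |
| 20% | 28.0 | 60.6% / 60.2% | 66.0% | 72.9% (34/17) |

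The non-responder column uses rates (1 − f) × 50% and (1 − f) × 15% at 42/21. The restricted column keeps 50% versus 15% at the smaller numbers.

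**4. What restriction recovers.** Restricted minus as written is 3.2–3.5 points at f = 5%, 5.5–6.0 at 10%, 7.8–8.2 at 15% and 12.3–12.7 at 20%. At 10%, 7.7 points of the fall (82.3 − 74.6) occur even when discordant subjects count as non-responders; a further 2.7–3.2 come from counting them as responders.

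**5. Chance imbalance.** At f = 10% the standard deviation of the between-arm difference in f is √[0.1 × 0.9 × (1/21 + 1/42)] = 8 points. A single dataset could tilt either way although the expected tilt is zero.

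**The case against.** **The word resolution implies NASH at baseline.** SAP 8.2.6 speaks of complete resolution and refers to baseline and Week 24, so the bracket can be read as defining only the resolved state. That is a fair reading. But the operational test contains no baseline inflammation or ballooning score, and a programmer following it would count these subjects. The text needs to settle it.

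**The baseline read is not named.** If the inclusion read were the baseline, every eligible subject would start with ballooning of at least 1 and the problem would disappear. The central read of both biopsies makes the central Screening score the more likely intent, but neither document says so. This stands, and is why the fix must name the read.

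**Redaction.** SAP 5.5 (Liver Histology Population) and the index of tables are blacked out, and the mock-ups are separate documents. A restriction could sit there. Protocol 12.4.6 has none, and the main analysis uses the Efficacy Population, so this lowers confidence without removing the point.

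**The dilution may be overstated.** The 50% came from the 3-mg group, whose biopsies fall under the same central-read rule. If it already includes subjects meeting the criterion at baseline, adding more on top counts them twice. This stands as a limit on the power figures.

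**Fewer at-risk subjects cost power in any case.** At 5% and 10% discordance, most of the loss remains when discordant subjects are non-responders. That also stands; the benefit of restriction is the smaller gain in step 4 of the working.

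**Conclusion.** The point holds as a gap in the definition of a secondary endpoint. As SAP 8.2.6 is written, and with the central Screening read as baseline, a subject can count as a NASH-resolution responder without any histologic change, and no visible population definition prevents it. Illustrative power falls from 82% to between about 77% and 60% for 5–20% discordance, against about 80% to 73% with restriction. This rests on assumed discordance, 60–80% persistence equal in both arms, composite planning rates applied to at-risk subjects, and 42/21 completers.

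A reader might infer more than the documents support:

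- **Bias toward NGM282.** The central reads are unpaired and blinded and allocation is random. The expected effect is dilution and inflated rates in both arms.
- **That the cohort was sized on resolution.** Protocol 12.1 takes its 50% from fibrosis improvement or resolution combined. A discordant subject can enter that composite through its resolution part, but no planning rate exists for resolution alone.
- **That the fibrosis endpoint needs a matching exclusion of central stage 0.** Enrolment requires stage 2 or 3, so this takes at least a two-stage disagreement, and keeping such subjects as non-responders is a defensible, conservative choice.
- **That the primary endpoint is affected.** It is MRI-PDFF liver fat and does not use these reads.

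**What to change.** Before unblinding, amend SAP 8.2.6 to:

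1. State that the central Screening read is the histology baseline.
2. Analyse NASH resolution, and the resolution part of any composite, in subjects who do not already meet the criterion on that read (ballooning at least 1 or inflammation at least 2).
3. Report the number of excluded subjects by arm.
4. Report the all-subject version as a sensitivity analysis.

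The restriction uses a blinded read of tissue taken before randomisation, so it keeps the randomised comparison valid. If redacted SAP 5.5 already contains it, a cross-reference from 8.2.6 is enough, provided that population is the one used for the resolution analysis. The cost is SAP wording and slightly smaller denominators: at 10% discordance, 38/19 instead of 42/21.

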### **9.9.2                    Magnetic Resonance Imaging (MRI)**

All enrolled subjects will have a Baseline (from the Screening result) and EOT MRI of the liver to evaluate liver volume and liver fat. Open-label single-blind cohort subjects are requested to undergo an additional MRI at Weeks 6 and 18.

Subjects in the placebo controlled 24-week histology cohort will have an MRI performed at Screening and at Weeks 6, 12, 24, and 30. None of the treatment or post treatment MRI results (other than incidental findings) will be provided to the sites. MRI-PDFF should be performed before the last dose of NGM282

MRI-PDFF will be reported on all MRI imaging scans. Scans should be performed at high field strength (3T preferred, 1.5T acceptable), without the administration of oral or intravenous contrast material. MRI examinations will include a six-echo gradient recalled echo (GRE) sequence (2D preferred, 3D acceptable), [REDACTED]  
[REDACTED]

The initial study MRI examination will be performed during the Screening period prior to randomization. An MRI-PDFF value of  $\geq 8\%$  at Screening as assessed by the central radiology core is one of the inclusion criteria for the study. Therefore, for patients who require a liver biopsy as part of the trial (for whom no recent liver biopsy is available), it is

recommended that liver biopsy be scheduled no sooner than 7 business days after (electronic) transmission of the screening MRI examination to the central radiology core to allow adequate time for processing and reporting of the result. MRI-PDFF results will be reported to the individual site no more than 5 business days after the MRI examination is received.

For both Screening and EOT/Early Withdrawal MRI examinations, subjects should consume nothing by mouth (NPO) for 4 hours prior to their MRI appointment. Medications and small amounts of water are acceptable.

Prior to MRI, all subjects should undergo safety assessment per institutional protocols and per the guidelines of the local Institutional Review Board. Subjects should be questioned regarding claustrophobia, pregnancy or potential pregnancy, size or weight exceeding the capabilities of the MRI system, metal implants, and other potential safety issues.

Detailed instructions for MRI procedures and provision of examination to a central reader will be presented in a separate MRI Manual.

LiverMultiScan™ imaging will be also be collected during the MRI to obtain the MRI-PDFF assessments in dosing Groups 3 or 4 of the open-label single-blind cohort and all subjects in the placebo-controlled 24-week histology cohort. This scan is optional and will only be performed where the imaging technology is available and adequate. The subjects will be required to stay in the MRI machine approximately 10 minutes longer than the standard MRI procedure. The software uses the images of the liver to calculate parameters that have been shown to correlate with histological measures of steatosis, hepatic iron overload, and fibrosis of the liver (Banerjee 2014). Additionally, an LIF score and corrected cT1 value are also calculated, both of which have been correlated to liver histology as well as predicting liver-related outcomes (Banerjee 2014, Pavlides 2016, Perspectum Diagnostics, data on file).

Detailed instructions for the LiverMultiScan™ software and provision of the imaging to a central reader will be presented in a separate manual.

[REDACTED]. There are no current imaging techniques that can directly detect the specific stage of fibrosis. Most attempt to detect fibrosis indirectly using proposed biomarkers which include: stiffness, diffusion, perfusion, metabolites, and image texture with the leading biomarker being liver stiffness (Younossi 2017). [REDACTED]

### **9.9.3 Pharmacokinetic Blood Sample Collection and Processing**

In all cohorts, blood samples for PK analysis of NGM282 levels will be collected before dosing on all study visits. On Day 1 and Week 12, an additional PK blood sample will be collected 2 hours post-dose ( $\pm 20$  mins). Additionally, in the open-label single-blind cohort, up to 8 subjects per dosing group in the single-blind open-label cohort will be given the option to participate in further PK sampling at pre-dose (Baseline) and at 1, 2, 4, 8, and 12 hours ( $\pm 20$  mins) after dosing on Day 1 (Baseline) and Week 6. Subjects participating in the PK sub-study will not obtain an additional 2-hour post-dose sample.

Processing, storage, and shipping instructions for these PK blood samples will be presented in the study Lab Manual.

